The number and proportion (%) of patients with 1 or more repeated Hb measures after baseline will be reported. The mean, median, minimum and maximum Hb values across all measures available after baseline for each patient will be calculated. The number and proportion (%) of patients with median and maximum Hb levels below the target level ( $\leq 10$  g/dL), in the target range ( $> 10$  to  $\leq 12$  g/dL)

and above the target level (> 12 g/dL) will be reported. Rapid increases in Hb level may increase the risk of thrombotic events. Therefore, the number and proportion (%) of subjects with a rise in Hb level of more than 2 g/dL in any 4-week period will be reported. Guidance from the SmPC is to regularly monitor Hb levels and reduce or interrupt the ESA dose if a rapid increase occurs, therefore the number and proportion (%) of subjects with a rise in Hb level of more than 2 g/dL in any 4-week period that had a subsequent ESA dose reduction or therapy interruption in their medical notes will be reported.

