#### 9.2.6 Study Follow-up

All information relating to an individual patient will be collected retrospectively using medical records. All ESA treatment episodes will be collected from the index date until 9 weeks post-index date or if 1 of the following criteria is met: ESA treatment end date, death, or date of consent/enrolment, whichever comes first.

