### 9.3 Variables

#### 9.3.1 Exposure Assessment

The main exposure for the study will be treatment with ESAs – either darbepoetin alfa or epoetin (any type). Information on use of an ESA treatment will be determined by the presence of 1 or more prescriptions for an ESA as recorded in the EMR, including time of each administration (if available), dose and type of ESA.

- Date of ESA prescriptions
- Type of ESA
- Frequency of ESA administration (where available)
- Dose of ESA
  - Recorded dose at each prescription
  - Dose modifications: recorded as raw values and categorised and reported as nominal categorical variables: dose increase/dose decrease/interruption.
- Total duration of ESA prescription will be calculated and expressed in number of weeks on treatment, and by number with prescription duration of 3, 4, 6, and 9 weeks.

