##### Secondary outcome

For Hb levels during treatment, all available measurements during ESA treatment will be collected per patient.

Hb values achieved at pre-specified time points during treatment (ie, 3 weeks, 4 weeks, 6 weeks, and 9 weeks) will be reported. These time points are in line with recommended dosing intervals of the SmPC and Study 20070782.

The baseline demographic and clinical characteristics of patients initiating treatment with an ESA and receiving myelosuppressive chemotherapy will be described as the number and proportion (%) for each of the covariates listed in Section 9.3.3.

The duration of prescription will be collected for each ESA prescription. The mean duration of prescription will be described, and the number and proportion (%) of patients with an ESA prescription at 3, 4, 6, and 9 weeks will be described.

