### 9.3.3 Covariate Assessment

- Demographics
  - Age, assessed at index as categorical in 5-year age bands: 18-20, 21-25, 26-30, 31-35, 36-40, 41-45, 46-50, 51-55, 56-60, 61-65, 66-70, 71-75, 76-80, 81-85, > 85
  - Sex
  - Country
- Clinical characteristics at index
  - Type of currently treated malignancy
  - Year of diagnosis for currently treated malignancy
  - Disease stage at diagnosis (nonmetastatic and metastatic)
  - Eastern Cooperative Oncology Group (ECOG) status
- Chemotherapy
  - Timing of administration
  - Drug(s) regimen
- Comorbidities
  - Hypertension
  - Acute liver disease
  - Chronic liver disease
  - Epilepsy
  - Sickle cell anaemia
  - Diabetes (1 and 2)
  - Thromboembolic events
  - Cardiac disease
  - Chronic pulmonary disease
  - Cerebrovascular disease
  - Peripheral vascular disease
  - Red cell aplasia
  - Chronic inflammatory disease (eg, rheumatoid arthritis, inflammatory bowel disease)
  - HIV or AIDS
  - Hepatitis B or C
- RBC transfusions
  - Count of RBC transfusions and number of units at baseline (in the last 3 months before index date)
  - Count of RBC transfusions during treatment

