##### Secondary endpoints

The baseline demographic and clinical characteristics of patients initiating treatment with an ESA and receiving myelosuppressive chemotherapy will be described as the number and proportion (%) for categorical variables, or as means, SD, median, min and max for continuous variables, for each of the covariates listed in Section 9.3.3, and stratified by ESA type, type of malignancy, and country.

The frequency of ESA treatment, the number of ESA prescriptions, and the duration of ESA prescriptions will be summarized with descriptive statistics overall and stratified by ESA type, type of malignancy, and country. The number and proportion (%) of patients prescribed an ESA for 3, 4, 6, and 9 weeks will be reported.

The starting dose will be summarized with descriptive statistics by ESA type. The number and proportion (%) of patients with at least 1 dose modification will be reported

overall, and (where available) by type of dose modification (eg, dose reduction, dose escalation, therapy interruption).

The number and proportion (%) of patients with 1 or more repeated Hb measures after baseline will be reported.

Hb values reached at pre-specified time points during treatment (ie, 3 weeks, 4 weeks, 6 weeks, and 9 weeks) will be described.

Hb values during treatment will be described in terms of:

- Mean, standard deviation, median, interquartile range, minimum, maximum values.
- The proportion of patients reaching the target Hb level, expressed as:
  - Below target level ( $\leq 10$  g/dL)
  - Target range ( $> 10$  to  $\leq 12$  g/dL)
  - Above target level ( $> 12$  g/dL)
- The proportion of patients at week 9 who:
  - Had a rise in Hb of more than 2 g/dL in any 4-week period
  - Had a rise in Hb of more than 2 g/dL in any 4-week period that did not have a subsequent ESA dose reduction or therapy interruption

Handling of multiple measurements per patients:

All Hb values as recorded within  $\pm 6$  days around each time point of interest (3, 4, 6, and 9 weeks) will be used to inform on the values to be reported for this study. The mean and median value for each patient will be calculated for each time point. For example, at 3 weeks (day 21), the mean and median of all Hb values recorded in days 15-27 will be calculated.

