#### **9.7.2.5 Sensitivity Analysis**

For the calculation of Hb values both at baseline and during treatment, we will perform a sensitivity analysis that excludes values from patients with RBC transfusions in the last 28 days from the recorded Hb value, in line with Study 20070782.

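### The rapid-rise/no-action endpoint requires no observable period after the rise, so rises first shown near day 63 count as no action; permanent stops and the week-9 denominator are also left unclear

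*Protocol*

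**What the plan says.** Under Secondary endpoints in Section 9.7.2.4, two proportions are introduced by "The proportion of patients at week 9 who". The first is of patients with a rise of more than 2 g/dL in any 4-week period. The second is of patients with a "rise in Hb of more than 2 g/dL in any 4-week period that did not have a subsequent ESA dose reduction or therapy interruption".

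Four other places bear on how these are computed:

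- **Follow-up (Sections 9.2.1 and 9.2.6).** ESA treatment episodes are collected to 9 weeks after index or, if earlier, to "ESA treatment end date, death, or date of consent/enrolment, whichever comes first".
- **Hb data (Section 9.3.2, Secondary outcome).** "all available measurements during ESA treatment will be collected per patient".
- **Dose changes (Section 9.3.1).** These are recorded as raw values and "categorised and reported as nominal categorical variables: dose increase/dose decrease/interruption".
- **The same endpoint elsewhere.** The objectives table in Section 5 and the list in Section 8.2 carry no week-9 limit. Nor does the data-analysis text of the abstract, where "the number and proportion (%) of subjects with a rise in Hb level of more than 2 g/dL in any 4-week period will be reported". That text then reports the patients whose rise was followed by an action, which is the complement of the quantity in Section 9.7.2.4.

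**The concern.** The abstract links rapid rises to thrombotic risk and to the product label's advice on monitoring and dose adjustment. This endpoint is the study's direct description of whether that advice is followed, and consistency with the label is a stated aim.

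The endpoint is defined by the absence of a later event, but the plan does not require that a later event could have been observed. Absence of a response and absence of observation fall into the same class. The result would overstate non-adherence, and the reader of the report could not tell by how much.

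Two gaps in definition add to this. Permanent discontinuation has no named place among the dose changes, so abstractors or programmers may classify like patients differently. The denominator can also be read in more than one way. Section 9.9.3 treats discontinuation only as a loss of precision for the secondary outcomes. For this endpoint, stopping may itself be the response of interest, so the issue is bias as well.

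**Working it through.** The protocol gives no expected rate or precision for this endpoint, so there is no stated figure to reproduce. The steps below combine its follow-up rule with labelled assumptions.

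**1. Which end of follow-up applies.** Eligibility requires at least 9 weeks between ESA initiation and enrolment or consent, so consent cannot cut follow-up before week 9. What remains is day 63 (9 × 7), the ESA end date, or death.

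**2. Late rises.** A rise shown by an Hb value on day d leaves 63 − d days for a recorded response, and none at d = 63. Assume that detection is uniform from day t0 to day 63 and that the next dosing decision comes L days later. The share of rises with less than one interval left is L / (63 − t0).

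| t0 | L = 7 | L = 14 | L = 21 |
|---|---|---|---|
| day 21 | 7/42 = 17% | 14/42 = 33% | 21/42 = 50% |
| day 7 | 7/56 = 12.5% | 14/56 = 25% | 21/56 = 37.5% |

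Both t0 and L are assumptions. The study includes any epoetin as well as darbepoetin alfa, and dosing frequency is recorded only where available. Patients whose follow-up ends before day 63 have less time than this.

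**3. Effect on the no-action share.** Let u be the true no-action share among patients with a rise, l the share whose action would fall after the cut, and s the share of actions that are permanent stops. If stops are not counted as interruptions:

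apparent share = u + (1 − u) × [l + (1 − l) × s]

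With u = 20% (assumed):

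- Late rises only (s = 0): l = 17% gives 0.20 + 0.80 × 0.17 = 34%; l = 33% gives 0.20 + 0.80 × 0.33 = 46%.
- Stops only (l = 0): s = 10%, 30% or 50% gives 28%, 44% or 60%. If stops are counted as interruptions, the share stays at 20%.
- Both, with s = 30%: l = 17% gives 0.20 + 0.80 × (0.17 + 0.83 × 0.30) = 53.5%; l = 33% gives 0.20 + 0.80 × (0.33 + 0.67 × 0.30) = 62.5%.

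Using the shares from step 2 as l assumes that each action comes one full interval after the rise is detected.

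**4. Denominator.** Suppose 60% of the planned 1625 patients (975) are still on an ESA at week 9.

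- Rise rate 10% in those on ESA and 20% in the rest: 10% if only those on ESA count, against 0.6 × 10% + 0.4 × 20% = 14% for all.
- Rates reversed: 20% against 16%.
- Equal rates: no difference.

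The direction is therefore unknown.

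**5. All patients or patients with a rise.** No section says which is the base for the no-action share. If 20% of patients with a rise have no action and 10% to 30% of all patients have a rise, the figure is 20% on one base and 2% to 6% on the other.

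**The case against.** Much can be said for the plan.

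- **Stops.** A reader might infer that the plan counts every stopped patient as having had no action. No section says so. A permanent stop could be coded as a therapy interruption, the list of modification types in Section 9.7.2.4 is given as examples, and the ESA end date is known because it ends follow-up. What stands is that the classification is left open, so a miscount is possible.
- **Week 9.** A reader might infer that the denominator is restricted to patients still on an ESA at week 9. The lead-in can equally mean cumulative to week 9, because the items beneath it refer to any 4-week period. Under the restrictive reading, stopped patients are dropped and cannot also be counted as no action, so the two effects cannot both apply to the same patient. What stands is the conflict in wording with Sections 5 and 8.2.
- **Transfusions.** A reader might infer that transfusion-driven rises go unaddressed because Section 9.3.3 lists only "Count of RBC transfusions during treatment". Section 9.7.2.5 already plans a sensitivity analysis that sets aside Hb results preceded by "RBC transfusions in the last 28 days from the recorded Hb value, in line with Study 20070782". A covariate list does not show that the eCRF lacks transfusion dates.
- **Statistical analysis plan.** Derivation rules are commonly left to that document, which is not at hand. The 9-week cut, however, is fixed in the protocol, and so is the class into which an unanswered rise falls. Nothing in the protocol removes the late-rise bias.

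**Conclusion.** The concern holds for late rises. With no required period after the rise and ESA data ending at day 63 at the latest, some rises are counted as unanswered when no answer could be observed. The direction is upward. The size is not known from the document: 12.5% to 50% of rises have less than one dosing interval left under the assumed detection ranges and intervals of 7 to 21 days.

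The place of permanent discontinuation, the meaning of the week-9 lead-in, and the choice between the action and no-action versions are defects of definition. They make the result depend on interpretation, but the document does not establish a particular bias from them.

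Severity is moderate. This is one descriptive secondary endpoint in an estimation study, and baseline Hb, the primary outcome, is not affected. No view is taken on any dosing rule.

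**What to change.** 1. Report the rise proportion among all patients with at least two Hb values no more than 28 days apart during follow-up. Delete the week-9 lead-in or restate it as cumulative through week 9.
2. For each patient with a rise, classify the recorded response as reduction, interruption, permanent discontinuation (from the ESA end date already collected), none, or not evaluable. Not evaluable means death, or follow-up that ended before any later ESA prescription or dosing record.
3. Report the no-action share among evaluable rises, with the not-evaluable count beside it so that readers can bound the result.
4. Reconcile the objectives table and data-analysis text in Section 5 with Section 9.7.2.4, so that all use the same quantity, direction and base.

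The cost is a slightly smaller denominator, one extra response category for discontinuation, a not-evaluable count, and aligned wording. Everything uses data already planned. Abstracting ESA dosing beyond week 9 is not proposed: it would change the defined follow-up and need an amendment with ethics approval under Section 12.1.

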### 9.2 Setting and Study Population

#### 9.2.1 Study Period

The study period is anticipated to include data spanning from January 2015 (based on updated guidance by the National Institute for Health and Care Excellence [NICE] at the end of 2014; NICE 2014) until last patient enrolled. Erythropoiesis Stimulating Agents treatment initiation (the prescription date) will be considered the study index date. Patients will be followed from the index date until 9 weeks post-index date or if 1 of the following criteria is met: ESA treatment end date, death, or date of consent/enrolment, whichever comes first. Baseline data to provide details on the patient’s medical condition prior to use of ESA may include data from medical records prior to January 2015.

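### The ±6-day Hb windows for weeks 3 and 4 share six days, and the week-9 window runs six days past the protocol's own end of follow-up

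*Protocol*

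**What the plan says.** In Protocol Section 9.7.2.4 (secondary endpoints, handling of multiple measurements), the half-width of each window is six days, and Hb values from those "days around each time point of interest (3, 4, 6, and 9 weeks) will be used to inform on the values to be reported". The worked example fixes both the width and the day convention: "For example, at 3 weeks (day 21), the mean and median of all Hb values recorded in days 15-27 will be calculated". Within a window, "The mean and median value for each patient will be calculated for each time point". No sentence says what happens to a value that lies in two windows.

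Section 9.2.1 sets the length of observation: "Patients will be followed from the index date until 9 weeks post-index date", or until ESA treatment ends, death, or consent/enrolment, if any of these comes sooner. Section 9.2.6 uses the same limit for treatment data: "All ESA treatment episodes will be collected from the index date until 9 weeks post-index date". Section 9.3.2 describes the scope of the Hb data as "all available measurements during ESA treatment will be collected per patient", without repeating the 9-week limit. Section 9.2.3.1 requires at least 9 weeks between ESA initiation and enrolment or consent.

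**The concern.** Weeks 3 and 4 are seven days apart, while each window reaches six days either side. The windows must therefore overlap, and nothing assigns a value to one of them only. A patient whose only Hb test in days 15-34 falls on day 24 contributes the same number to both time points. Section 9.3.2 ties the choice of time points to the dosing intervals of the SmPC and Study 20070782, so weeks 3 and 4 are meant to be told apart, and the window rule blurs them.

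At week 9 the window is centred on the last possible day of follow-up, so its upper half lies outside the observation period. A result labelled week 9 would come from the week before. A patient whose test falls just after day 63 drops out, for a reason that the discussion of missing Hb in Section 9.9.3 does not mention.

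At stake are the Hb summaries at weeks 3, 4 and 9. They serve a stated secondary objective (Section 8.2), are repeated by ESA type, tumour and country (Section 9.7.2.5.1), and enter the transfusion sensitivity analysis (Section 9.7.2.5).

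**Working it through.** **Inputs.** Time points at weeks 3, 4, 6 and 9 and a half-width of 6 days (Section 9.7.2.4); 3 weeks = day 21, hence week w = day 7w (worked example, same section); end of follow-up 9 weeks after index at the latest (Sections 9.2.1 and 9.2.6), which is 9 × 7 = day 63.

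**Step 1: reproduce the protocol's figure.** Window for week w = 7w − 6 to 7w + 6, both ends included, 13 days. For week 3: 21 − 6 = 15 and 21 + 6 = 27. This matches the stated days 15-27.

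**Step 2: the other windows.**

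| Time point | Target day | Window |
|---|---|---|
| Week 3 | 21 | 15-27 |
| Week 4 | 28 | 22-34 |
| Week 6 | 42 | 36-48 |
| Week 9 | 63 | 57-69 |

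**Step 3: overlap.** Weeks 3 and 4 share days 22-27, which is 6 days; 6/13 = 46% of each window. No other pair overlaps.

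**Step 4: week 9 against the follow-up cap.** Days 64-69 lie after day 63: 6 of 13 days, 46%. Days 57-63 remain: 7 days, midpoint (57 + 63)/2 = day 60, three days before the nominal day. If the day count of the cap is shifted by one, the part outside is 5/13 = 38% or 7/13 = 54%; the protocol's own convention gives 6/13.

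**Step 5: what this means for patients at week 9.** The summary uses every value in the window, so a patient with any test on days 57-63 stays in. The protocol gives no test frequency. Assume tests every T days, a starting day that is equally likely anywhere in the cycle, and treatment throughout. The chance of at least one test in a window of k days is then min(1, k/T), and the relative loss of patients is 1 − min(1, 7/T) / min(1, 13/T):

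- T = 7: 1 − 1/1 = 0%
- T = 10: 1 − 0.70/1 = 30%
- T = 13: 1 − (7/13)/1 = 46%
- T above 13: 1 − 7/13 = 46%

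**Step 6: what a three-day shift could mean in Hb.** For scale only, take Hb rising at the protocol's own rapid-rise threshold of 2 g/dL in 28 days: 3 × 2/28 = about 0.2 g/dL.

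**Step 7: windows without overlap.** The midpoint between days 21 and 28 is 24.5. Assigning each value to its nearest time point gives week 3 = days 15-24 and week 4 = days 25-34, 10 days each, none shared. Week 6 is unchanged. Narrowing the half-width would also work, but only at ±3 or less: ±5 still shares 4 days and ±4 shares 2, while ±3 leaves 7 of 13 days per window.

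**The case against.** The strongest reply is that little depends on these windows. This is an estimation study, and no week-3 to week-4 comparison is planned; values at each time point are only described. Nothing pools the time points, so no total is inflated by a shared value. The primary outcome is Hb at index. The rapid-rise endpoint looks at any 4-week period and is not defined on these windows, and the abstract (Section 5) takes the target-range categories from each patient's median and maximum over all post-baseline values. All of this stands, and it confines the point to secondary descriptive summaries.

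Three stronger readings are tempting, and the document does not support them:

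- *The week-3 to week-4 change is forced to zero.* It is attenuated. It is exactly zero only for a patient whose values at both time points all come from days 22-27.
- *Hb on days 64-69 is never collected.* That is the likely reading of Sections 9.2.1 and 9.2.6, but it is not stated for Hb, because Section 9.3.2 does not repeat the cap. Even so, ESA episodes are not collected beyond 9 weeks, so whether a later value is on treatment could not be established. The sections are unreconciled on either reading.
- *46% of week-9 patients are lost.* The 46% is a share of window days and the upper end of a range that starts at about zero.

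It may also be said that a statistical analysis plan could add an allocation rule. It could, but the point does not rest on an omission: the protocol itself states the window rule, and that rule creates the overlap and conflicts with the protocol's follow-up limit.

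**Conclusion.** The point holds for the secondary Hb summaries. As written, the rule uses any Hb value on days 22-27 at both week 3 and week 4 (6 of 13 days, 46% of each window), so the two rows are partly the same data. The week-9 window conflicts with the 9-week cap on follow-up: 6 of its 13 days fall outside, and the summary in effect describes days 57-63, centred on day 60. The relative loss of patients at week 9 is between about 0% and 46%, depending on test frequency; that range assumes regular testing and continued treatment. The day counts rest only on the protocol's convention that 3 weeks is day 21. The primary outcome and the rapid-rise endpoint are unaffected. The fault is modest, but the rule is wrong as stated and cheap to correct, so it should be put right before the primary analysis.

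**What to change.** In Section 9.7.2.4, keep the per-patient mean and median and add that each Hb value counts only at its nearest time point: week 3 = days 15-24, week 4 = days 25-34, week 6 = days 36-48. Replace the worked example accordingly. State week 9 as days 57-63 and label it so in the tables, in line with Sections 9.2.1 and 9.2.6. Say in Section 9.3.2 that the 9-week limit also applies to Hb.

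**Cost.** The week-3 and week-4 windows each fall from 13 to 10 days, so some patients will have a value at one of the two time points only. No further chart abstraction is needed. The text change goes through the amendment process in Section 12.1, including ethics approval.

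**Alternatives that cost more.** Windows of ±3 days also remove the overlap but discard 6 of 13 days (46%) at each time point. Collecting Hb to day 69 would restore a symmetric week-9 window. It would, however, also need ESA episodes and transfusions beyond the present cap and might mean reopening charts, since data collection is planned from January 2023 to September 2024 (Section 4). Eligibility secures only 9 weeks before consent, so the later days would still not be available for every patient.
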